7.2.1 Full Analysis Set (FAS)

All subjects who have been randomized and has a confirmed diagnosis of Acanthamoeba keratitis and for whom the primary efficacy variable has been assessed will be included in the FAS. The FAS will be used in all efficacy analyses. The last disease status assessment will be used for disease status assessment.

Analysis using the FAS will be based on the planned treatment (i.e. subjects will be analysed 'as randomised').

7.2.2 Per-Protocol Analysis Set (PPAS)

The per-protocol analysis set is defined as the subset of subjects in the FAS for whom no major protocol deviation judged as having an impact on the primary efficacy analysis was reported or identified. The last disease status assessment within 12 months of randomisation will be used for disease status assessment. For subjects with disease resolution at that last visit, the 30-day and 90-day follow-up assessments should confirm disease resolution. Otherwise, the disease will be regarded as not having been resolved.

The decision as to which protocol deviations should be considered as reason for exclusion from the PPAS should be made at the clean file meeting and documented in the clean file report.

Analysis on the PPAS will be based on the actual treatment (i.e. subjects will be analysed 'as treated'). The primary efficacy variable, CRR_12, will also be evaluated using the PPAS.

7.2.3 Safety Analysis Set

All subjects who have received at least one dose of study medication will be included in the Safety Analysis Set. This set will be used in all analyses of safety data.

Analysis on the safety analysis set will be based on the actual treatment (i.e. subjects will be analysed 'as treated').

7.3 Disposition of Subjects

The following will be presented:

- Number of screened subjects, in total, if available.
- Number of screening failures, in total, if available.
- Number of randomised subjects, by treatment group and in total.

Based on the number of randomised subjects, the following will also be presented, by treatment group and in total:

- Number and percentage of subjects who did not meet randomisation inclusion/exclusion criteria
- Number and percentage of subjects who did not receive any dose of IMP.
- Number and percentage of subjects who received at least one dose of IMP.
- Number and percentage of subjects who completed the required treatment.
- Number and percentage of subjects who withdrew prematurely from the study, i.e. withdrew before completing the follow-up visits.
- Number and percentage of subjects in each of the analysis sets.

In addition, a frequency table on the primary reason for premature withdrawal from the study will be presented by treatment group and in total. Percentages for this table will be based on the number of prematurely withdrawn subjects.

The number of subjects attending each study visit will also be summarised.

7.4 Protocol Deviations

Protocol deviations will be presented in a data listing.

The number and percentage of randomized subjects with at least one major protocol deviation leading to exclusion from an analysis set will be presented.

Major deviations are those deviations that could affect the scientific integrity of the study:

- Did not comply with the allocated treatment
- Did not attend the two follow-up visits

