5.2. Drug dosage and Administration

On Day 0, subjects will receive instructions on how to apply the eye drops. Subjects will receive the assigned treatment to be administered in the affected eye until resolution. Subjects will be treated for a maximum of 1 year after randomization and subjects meeting the criteria for clinical resolution at or before 12 months will be followed up for 90 days before completing the study.

Subjects will receive an initial intensive course of 0.08% PHMB + placebo or 0.02% PHMB + 0.1% propamidine combination therapy.

Treatment throughout the study will be given using 1 drop of each ophthalmic solution in the study eye at different frequencies during the daytime only. At study entry, an intensive 19-day antiamoebic treatment protocol will be initiated as follows:

Day 0 to 5*	1-hourly drops (16 drops in a day) for 5 days
Day 6 to 12	2-hourly drops (8 drops in a day) for 7 days
Day 13 to 19	3-hourly drops (6 drops in a day) for 7 days
Day 20	Then 4x daily thereafter

^{*} on the first day of treatment (after randomization) 16 drops might not be feasible, in this case the treatment should be applied as many times as possible but not exceeding the hourly regimen.

Notes on treatment

- i. The frequency will be maintained at 4x daily unless there is a relapse (see Box XI, Relapse on page 42). In the event of a relapse, culture negative subjects will receive the same intensive 19-day treatment course as given at study entry.
- ii. Antiamoebic drops will be discontinued when clinical resolution is reached (see Figure 2 and Legend IV Discontinue treatment).
- iii. Clinical resolution is a clinical definition, resulting from a slit lamp examination, with the following findings:

- No corneal inflammation (including subepithelial infiltrates, stromal infiltrates and oedema) that requires treatment, with a healed corneal epithelium and minimal punctate staining (10 dots or less equivalent to Grade 1 on the Oxford Scale).
- No or mild conjunctival inflammation (including bulbar injection, bulbar oedema, tarsal hyperemia): mild conjunctival inflammation is acceptable if related to other concurrent conditions such as blepharitis.
- No limbitis, scleritis or anterior chamber inflammation.

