5.3. Treatment and Follow-up Protocol

A schematic overview of the treatment and follow-up period is presented in figure 2.

[figure not shown]

Figure 2: Schematic Presentation of the Treatment and Follow-up Protocol

Legend for Figure 2 - The text boxes and lines in the figure are color coded:

- Pale blue text boxes and lines for responding disease or treatment success and STUDY END POINT
- Red text boxes and lines for poorly responsive and recurrent / relapsing disease presumed to be due to replication of *Acanthamoeba*
- Pink text box for exacerbations of inflammation presumed to be due to flare ups of inflammation secondary to the immune response to non-viable *Acanthamoeba*
- Black text boxes for treatment failure endpoints ALL leading to TRIAL EXIT

This protocol defines the treatment of patients. Treatment options are defined as far as possible to reduce variations, which will complicate or invalidate the analysis of the results, whilst maintaining optimal standards of care based on current evidence and expert opinion. The changes of therapy in this protocol, and therapeutic failures, are determined by both the development and resolution of clinical signs of inflammation and ulceration, as well as the identification of *Acanthamoeba* by culture during disease relapses.

Each box is labelled with a Roman numeral I to XVIII. The legend below describes the rationale for each step:

BOX I. FOLLOW UP PROTOCOL from day zero at TRIAL ENTRY.

Treatment throughout the study is given using 1 drop of each ophthalmic solution in the study eye at different frequencies during the daytime only.

At study entry initiate an intensive 19-day antiamoebic treatment protocol:

Day 0 to 5

1-hourly drops (16 drops in a day) for 5 days

Day 6 to 12

2-hourly drops (8 drops in a day) for 7 days

Day 13 to 19

3-hourly drops (6 drops in a day) for 7 days

Day 20

then 4x daily thereafter

- a. This frequency is maintained at 4x daily unless a relapse (BOX XI RELAPSE) occurs. In case of a relapse, culture negative subjects receive the same intensive 19-day treatment course as given at study entry.
- b. Antiamoebic drops are discontinued when IV DISCONTINUE TREATMENT is reached.

In subjects on steroids at TRIAL ENTRY: (already using topical steroids for e.g. mistaken diagnosis of HSV keratitis or as adjunctive treatment for bacterial keratitis), the same intensive 19-day antiamoebic treatment protocol is used. For their steroid use there are these options:

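### Read literally, SAP 7.4 makes missing the two follow-up visits a major deviation even for treatment failures, who exit before those visits are due, so per-protocol membership could depend on the outcome

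*SAP*

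**What the plan says.** - **SAP 7.4** gives two examples of deviations that could affect scientific integrity: non-compliance with the allocated treatment, and "Did not attend the two follow-up visits". It ties major deviations to analysis sets by requiring that the number of subjects with "at least one major protocol deviation leading to exclusion from an analysis set will be presented".
- **SAP 7.2.2** builds the PPAS from FAS subjects "for whom no major protocol deviation judged as having an impact on the primary efficacy analysis was reported or identified". It adds: "The decision as to which protocol deviations should be considered as reason for exclusion from the PPAS should be made at the clean file meeting". For subjects resolved at their last visit within 12 months, the 30- and 90-day assessments should confirm this. "Otherwise, the disease will be regarded as not having been resolved".
- **Protocol 5.2** says who has the follow-up: "subjects meeting the criteria for clinical resolution at or before 12 months will be followed up for 90 days before completing the study".
- **Protocol 5.3** describes the other branch of the flow chart: "Black text boxes for treatment failure endpoints ALL leading to TRIAL EXIT". Footnote 4 of the Schedule of Assessments ends the study for a failure at unmasking or after 12 months of treatment.
- **SAP 7.3** counts leaving before the follow-up visits are completed as premature withdrawal.
- **SAP 7.9** calls the PPAS supportive. **SAP 7.9.1** makes similar FAS and PPAS p-values and confidence intervals a condition for the non-inferiority claim.

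**The concern.** The two follow-up visits are counted from the end of treatment and exist to confirm a resolution already recorded. A subject who fails normally never has them. If non-attendance alone is a major deviation, failing treatment is enough to acquire one, and the PPAS becomes a set selected on the primary outcome.

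This matters because the SAP relies on the PPAS as a check. SAP 7.9.1 asks for agreement between the two sets because the FAS is generally not conservative in a non-inferiority setting. A PPAS made up almost entirely of cured subjects cannot show inferiority, and it cannot show superiority either.

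**Working it through.** **The plan's own figure.** Inputs from Protocol 7.6: control CRR_12 63%, test 83%, two-sided alpha 0.10, power 80%, 10% loss.

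n per arm = (1.645 + 0.842)² × (0.63×0.37 + 0.83×0.17) / 0.20² = 6.183 × 0.3742 / 0.04 = 57.8, so 58 per arm and 116 in total. 116/0.9 = 128.9, close to the stated 130. SAP 5.1 also gives 116 evaluable. The sample size is not in question. I use 58 per arm below.

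**PPAS under the literal rule.** Let p be the true cure rate and r the share of subjects attending both visits who have relapsed by day 90. The documents give no value for r, so I take 0%, 5% and 10%, equal in both arms.

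- PPAS size per arm = 58p/(1 − r)
- PPAS cure rate = 1 − r
- PPAS difference = (1 − r) − (1 − r) = 0 for any p. If r differed between arms, the difference would equal the gap in late relapse, still not the gap in cure.

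At r = 0 the arms hold 58×0.63 = 36.5 control subjects and 58×0.83 = 48.1 test subjects (or 58×0.43 = 24.9 if the test drug is 0.20 worse), all cured.

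**If the meeting keeps a share s of the failures** (r = 0), the PPAS rate is p/(p + s(1 − p)):

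| s | Control, p = 0.63 | Test, p = 0.83 | Difference | Test, p = 0.43 | Difference |
|---|---|---|---|---|---|
| 0% | 100% | 100% | 0 | 100% | 0 |
| 10% | 94.5% | 98.0% | +0.035 | 88.3% | −0.062 |
| 25% | 87.2% | 95.1% | +0.079 | 75.1% | −0.121 |
| 50% | 77.3% | 90.7% | +0.134 | 60.1% | −0.172 |
| 100% | 63% | 83% | +0.20 | 43% | −0.20 |

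Only keeping all failures recovers the design rates.

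**Decision rates.** 200,000 simulated trials per scenario, 58 per arm, Wald 90% interval for the difference (SAP 7.9.1 names both a 90% and a 95% interval; I follow the 90% one).

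| True rates (control, test) | Criterion | FAS | PPAS, r = 0% | r = 5% | r = 10% |
|---|---|---|---|---|---|
| 63%, 43% | lower limit above −0.20 | 4.3% | 100% | 94% | 83% |
| 63%, 43% | FAS and PPAS both above −0.20 | – | 4.3% | 4.3% | 4.3% |
| 63%, 83% | lower limit above 0 | 81% | 0% | 4% | 4% |

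With 65 per arm the PPAS-alone non-inferiority rates are 100%, 95% and 86%, and the joint rate is about 4.5%. FAS superiority is 84%, and PPAS superiority stays at or below 5%.

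**The case against.** The strongest reply is that a failure who exits as instructed has not deviated: a visit that was never due cannot be missed. SAP 7.2.2 points the same way, because it ties the follow-up assessments to resolved subjects and gives unconfirmed ones a not-resolved outcome inside the PPAS. That is a sensible reading and probably the intended one. But SAP 7.4 does not say it, and SAP 7.3 labels leaving before those visits as premature withdrawal. The 7.2.2 sentence covers subjects resolved at their last visit, so it does not exempt failures from 7.4.

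A reader might infer that failures are removed automatically. The documents do not support that. Only deviations judged to affect the primary analysis lead to exclusion, and the clean file meeting decides, before the blind is broken and with reasons recorded. Some failures may also stay in safety follow-up on open trial drug (Protocol 5.3.3). Judgement is still a weak safeguard here: Protocol 5.3.3 has the sponsor open the allocation when a failure exits, so for these subjects the decision may not be blind.

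A reader might also infer that the rule inflates false non-inferiority claims. It does not. The FAS is primary, and the joint rate stays at about 4–5%.

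Finally, it can be argued that a PPAS near 0 would visibly disagree with an FAS near −0.20 and so block the claim. That is true when the FAS is near −0.20. But the FAS passes only when its observed difference is above about −0.05: the half-width is 1.645 × √[(0.63×0.37 + 0.58×0.42)/58] = 0.149, and −0.20 + 0.149 = −0.051. A PPAS near 0 would then look similar, so the condition would be least informative where it is needed. The SAP gives no tolerance for similarity.

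**Conclusion.** The concern holds as a drafting fault in SAP 7.4 that conflicts with 7.2.2. Applied as written, the rule selects the PPAS on the outcome and gives cure of about 90–100% in both arms and a difference near 0, so agreement or disagreement with the FAS would say little about the treatments. At a true +0.20 the PPAS would find superiority in at most about 5% of trials against 81–84% in the FAS, so a drafting fault could also count against an effective drug.

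These sizes are the literal worst case. They assume that no failure without both visits is kept, that late relapse is 0–10% and equal between arms, and that there are no other exclusions. The effect shrinks as the meeting keeps more failures. The primary FAS analysis, the sample size and the false non-inferiority rate are not affected.

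**What to change.** Before the code is broken, amend the SAP as follows:

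1. In 7.4, limit the deviation to subjects with recorded clinical resolution who stopped treatment and for whom the 30- and 90-day visits were due.
2. State whether missing one visit is enough or both must be missed.
3. State that treatment failures are never excluded for this reason and stay in the PPAS as not cured.
4. Align 7.4 with 7.2.2 for resolved subjects whose resolution was not confirmed: either they are excluded, or they stay in as not resolved, but not both.

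The cost is a few sentences in 7.4 and 7.2.2. Nothing changes for sites, subjects or data collection. With no other exclusions, the PPAS then recovers the design rates (63% against 83%, or 63% against 43% at the margin).

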7.5 Demographics and Baseline Characteristics

Summary statistics and frequencies on demographic data (age and sex) will be presented for all analysis sets.

In addition, the summary of Best sphere (dioptres) will be summarised for the following categories:

Hypermetropes (Refraction greater than 0)

Emmetropes (Refraction equal to 0)

Myopes (Refraction less than 0)

7.6 Medical History and Concurrent Diseases

Medical history and concurrent diseases will be coded according to the latest available version of Medical Dictionary for Regulatory Activities (MedDRA).

For each system organ class and preferred term, the number and percentage of subjects with at least one condition in that system organ class or preferred term will be presented. Medical history and concurrent diseases will be presented in separate tables, based on the safety analysis set.

Medical history is defined as events stopped prior to study inclusion. Concurrent diseases are defined as ongoing events and events stopped on or after baseline. If the start and/or stop date is partially unknown, the following imputation rules will be used for the purpose of classifying the events:

Table: Imputation of missing parts of dates

	Imputed start date	Imputed end date
Unknown year	Missing	Missing
Unknown month	1 January	31 December
Unknown day	First of month	Last of month

If it is not possible to classify the condition based on the reported and/or imputed start and end dates, it will be considered as concurrent. In data listings, the dates will be presented as reported.

7.7 Prior and Concomitant Medication

Medications will be coded according to the World Health Organization (WHO) anatomical therapeutic chemical (ATC) classification system and summarized by therapeutic subgroup (ATC level 2) and preferred name.

For each therapeutic subgroup and preferred name, the number and percentage of subjects who used at least one medication of that therapeutic subgroup or preferred name will be presented. Prior and concomitant medications will be summarized in separate tables, based on the safety analysis set.

If a reported medication cannot be coded with a preferred name, the lowest available higher-level dictionary term will be used instead in the summary tables. If a medication cannot be coded on a lower level than the therapeutic subgroup or the anatomical main group (ATC level 1), that medication will be presented as 'Not codable' under that therapeutic subgroup/anatomical main group.

Prior medication is defined as medication stopped prior to baseline. Concomitant medication is defined as ongoing medication or medication stopped on or after baseline. If the start and/or stop date is partially unknown, the following imputation rules will be used for the purpose of classifying the medication:

	Imputed start date	Imputed end date
Unknown year	Missing	Missing
Unknown month	1 January	31 December
Unknown day	First of month	Last of month

If it is not possible to classify a medication based on the reported and/or imputed start and end dates, it will be considered as concomitant. In data listings, the dates will be presented as reported.

LINK Medical Study ID: PSR012

7.8 Compliance

Subjects who miss up to 1 full day of treatment within the first 5 days after starting treatment or up to 2 full days of treatment after the first 5 days of treatment should not be discontinued but will be classified as non-compliant. Subjects will be discontinued from the study if in the opinion of the investigator drug compliance is insufficient.

The rate of compliance with the IMP will be summarised for the FAS. The reasons will be listed.

7.9 Efficacy Evaluation

All efficacy evaluations will be based on the FAS. The PPAS will be used for supportive sensitivity analysis of the primary efficacy variable.

7.9.1 Primary Efficacy Variable

The main endpoint disease resolution 12 months after baseline will be assessed at each visit up to study day 365.

Clinical resolution 12 months after baseline for a patient is defined as:

The percentage of subjects cured 30 days after discontinuing all study therapies, within 12 months of randomization. A clinical resolution classification requires a Yes response to the eCRF variable CRYN question: "Was clinical resolution obtained?" at one of the study visits from day 1 up to study day 365 in combination with a response *No* to the eCRF variable RELAPYN question "Did the subject experience relapse since the last visit?" at the pursuing visits, up to the last recording of this information. There should be no relapses after (the last) clinical resolution classification. Discontinued subjects will be regarded as not cured.

For patients defined as fulfilling disease resolution within 12 months, the date of the visit at which annotated CRYN is first answered with a Yes will be used as the date of resolution. The time-to-cure secondary variable will be the number of days from randomisation to the visit where resolution was recorded.

Since it is also possible to test for non-inferiority if the superiority hypothesis is not met, additional conditions are specified (see list below) to meet the strict requirements of a non-inferiority study, making it feasible to test for non-inferiority using the results from the superiority analysis, without a further separate analysis. The 90% CI for the difference between the treatments obtained from the superiority analysis gives the necessary information. Position of the lower end of the CI relative to a pre-defined agreed 0.20 non-inferiority margin (Δ) provides the key information for making decisions (conclusions) about non-inferiority.

PHMB has received the orphan drug designation. The use of 90% CI for the difference between the two treatments is to provide a 95% lower CI limit for non-inferiority.

The additional conditions specified to make testing for non-inferiority feasible are the following:

- Pre-defined non-inferiority margin (Δ =0.20) based on both clinical and statistical considerations, i.e., chosen on the basis of external information and not chosen to fit the data.
- Analysis of the FAS and the PPAS, giving similar results with respect to p-values and CIs for the
 efficacy measure at issue.
- Study design and implementation directed at minimizing deviation from protocol (a particularly important source of bias in non-inferiority studies), e.g. special care to minimize violations of: entry criteria; non-compliance; withdrawals; loss; missing data; etc. This should help ensure the second bullet point.
- Evidence that the standard treatment is showing its usual (expected) level of efficacy.

These specifications are in accord with the recommendations by the Committee for Proprietary Medicinal Products, in document *Points to consider on switching between superiority and non-inferiority* (CPMP) 482/99. The recommendation regarding similar results with respect to p-values and CIs is founded on that the FAS "is generally not conservative and its role should be considered very carefully" in non-inferiority trials.

Null hypothesis difference:

No difference between test treatment and reference treatment

Non-inferiority clinical studies aim to demonstrate that the test treatment is no worse than the reference by more than a pre-specified small amount.

Null hypothesis non-inferiority:

• Test treatment is inferior to the reference by Δ or more

CRR_12 will be analysed using a general linear model (GLM) approach with treatment as factor to estimate the difference between success rates for the treatments, and test for difference between treatments. This will be the primary test of efficacy. The new treatment will be declared as non-inferior to the 0.02% PHMB + 0.1% propamidine combination therapy, if the lower limit of the 95% CI satisfies the requirement of a non-inferiority margin of Δ =0.20. The effects of covariate variables on the success rate will also be assessed using the GLM model with treatment, age and sex as explanatory variables. Further explorative analyses will be conducted by adding other, selected variables such as steroid use before treatment start, to the GLM model.

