1.2. Overall Rationale for the Study

Acanthamoeba keratitis is difficult to treat. If left untreated, the condition results in blindness or corneal transplant surgery in most patients (only 1 of the first 20 patients reported before the introduction of biguanide therapy had a good outcome, 3 had medical cures of whom 1 required a corneal transplant, 3 had their eyes removed and another 14 had 1 or more therapeutic corneal transplants. There are currently no drugs that are licensed for use in Acanthamoeba keratitis. The diamidines and biguanides are currently the most effective cysticidal anti-amoebic agents. However, the biguanides have the best amoebicidal and cysticidal activity. As a result, the current approach for the treatment for Acanthamoeba keratitis includes biguanides (PHMB or chlorhexidine) with or without the addition of diamidines (propamidine or hexamidine). The combination of 0.02% PHMB and 0.1% propamidine is the most commonly used combination. However, cases with a very poor clinical response have been reported. Section failures are possibly related to poor drug penetration into the deep cornea. The bioavailability of PHMB in the corneal stroma is likely to be increased by increasing the concentration of PHMB above 0.02%. Therefore, the use of PHMB 0.08% can be expected to reduce the treatment failures seen with PHMB 0.02%.

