5.3.4. End of Study

XIX. Summary of Study end points.

End-of-study is defined as the last follow-up visit at 90 days after end of treatment, or the day of study discontinuation. Discontinuation because of clinical failure is defined as follows:

- 1. Clinical resolution not achieved after 1 year of study treatment
- 2. Clinical relapse within 3 months after end-of-treatment, if occurring more than 12 months after randomization

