6.4. Secondary Variables

The secondary efficacy variables are:

- BCVA
- Corneal scarring as identified by slit lamp examination
- Ulceration severity as identified by slit lamp examination using a 2 grade scoring procedure; i.e. present or absent
- Anterior chamber inflammation as identified by ophthalmoscopy using a 3 grade scoring procedure
- EQ-5D questionnaire
- VFQ25 questionnaire

The secondary safety variables are:

- Adverse events
- Clinical laboratory tests
- Intraocular pressure (IOP)
- Ophthalmoscopy
- Worsening of the corneal epithelial defect and definable inflammatory signs (development of ring abscess and hypopyon) despite >30 days of treatment with the study drug)
- Rate of subjects with a relapse
- Rate of subjects requiring surgery, including amniotic membrane transplants, superficial keratectomy, application of cyanoacrylate glue, therapeutic penetrating, lamellar keratoplasty, cataract surgery, evisceration, or enucleation
- Rate of subjects requiring non-study therapies, e.g., topical steroids and NSAIDs
- Rate of subject discontinuation from study: to permit alteration of anti-amoebic therapy or for other unrelated specified reasons.
- Incidence of secondary complications, such as significant corneal neovascularization, corneal scarring, corneal perforation, scleritis, secondary glaucoma, cataract, retinopathy.

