3.1 Definitions

Clinical resolution is a clinical definition, resulting from slit lamp examination, with the following findings:

- No corneal inflammation (including subepithelial infiltrates, stromal infiltrates and oedema) that
 requires treatment, with a healed corneal epithelium and minimal punctate staining (10 dots or less
 equivalent to Grade 1 on the Oxford Scale).
- No or mild conjunctival inflammation (including bulbar injections, bulbar oedema, tarsal hyperemia): mild conjunctival inflammation is acceptable if related to other concurrent conditions such as blepharitis.
- No limbitis, scleritis or anterior chamber inflammation.
- No relapse within 30 days of discontinuing all topical and systemic therapy given for Acanthamoeba keratitis.

For regulatory and verification reasons there is an additional 60-day follow-up to exclude late relapses.

The CRR_12 is the clinical resolution rate at 12 months from randomisation and is defined as the percentage of subjects cured 30 days after discontinuing all study therapies, with 12 months of randomisation. This is the primary outcome measure. Subjects whose disease has not resolved at 12 months are considered treatment failures per protocol.

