3.2.1 Primary Variables

The primary efficacy variable is the CRR 12.

The CRR_12 is the clinical resolution rate at 12 months from randomization and is defined as the percentage of subjects cured 30 days after discontinuing all study therapies, within 12 months of randomization.

Criteria for clinical resolution:

A subject will be considered cured if resolution or absence of all the following clinical signs is confirmed by a slit lamp examination:

LINK Medical Study ID: PSR012

- No corneal inflammation (including subepithelial infiltrates, stromal infiltrates and oedema) that
 requires treatment, with a healed corneal epithelium and minimal punctate staining (10 dots or less
 equivalent to Grade 1 on the Oxford Scale).
- No or mild conjunctival inflammation (including bulbar injection, bulbar oedema, tarsal hyperemia): mild conjunctival inflammation is acceptable if related to other concurrent conditions such as blepharitis.
- No limbitis, scleritis or anterior chamber inflammation. No relapse within 30 days of discontinuing all topical and systemic therapy given for *Acanthamoeba* keratitis.

For regulatory and verification reasons, there is an additional follow-up at Day 90 after last treatment to exclude late relapses. Subjects whose disease has not resolved at 12 months are considered treatment failures per protocol.

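### The CRR_12 scoring rule does not say how therapeutic corneal surgery counts, so a grafted or keratectomised study eye can be scored as a cure

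*SAP*

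**What the plan says.** **Cure.** SAP 3.2.1: "A subject will be considered cured if resolution or absence of all the following clinical signs is confirmed by a slit lamp examination". SAP 3.1 and Protocol 2.1 add "No relapse within 30 days of discontinuing all topical and systemic therapy given for" *Acanthamoeba* keratitis. That condition concerns drug therapy and does not mention procedures. Protocol 6.3 lists the slit-lamp signs only.

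**Scoring rule.** SAP 7.9.1: "A clinical resolution classification requires a Yes response to the eCRF variable CRYN question" at a visit up to day 365, with RELAPYN answered No from then on. Two further sentences close the rule: "There should be no relapses after (the last) clinical resolution classification" and "Discontinued subjects will be regarded as not cured".

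**Failure and exit.** Protocol 5.3.2 and 5.3.3 name continued deterioration (Box X), culture-positive relapse (XIV), unresponsive scleritis (XV), and relapse after day 335 or active disease at day 365 (XVI). Protocol 5.3.4 gives two items: "Clinical resolution not achieved after 1 year of study treatment", and a late relapse after treatment has ended. Protocol 4.4 lists withdrawal reasons and SAP 7.4 lists major deviations. None of these names surgery. Protocol 4.2 excludes urgent need for surgery, but only at entry.

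**Surgery on study.** Protocol 6.4 makes it a safety variable: "Rate of subjects requiring surgery, including amniotic membrane transplants, superficial keratectomy, application of cyanoacrylate glue, therapeutic penetrating, lamellar keratoplasty", followed by cataract surgery and eye removal. SAP 7.10.9 tabulates it from CMTRT, the field that names any prior or concomitant drug or therapy. Discontinuation is a separate variable (SAP 7.10.11).

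**Margin.** Protocol 7.4.1.1.1 and SAP 7.9.2 take 1/20 as the cure rate without treatment. Protocol 1.2 describes the 20 patients: three medical cures (one of them grafted), three eyes removed, and "another 14 had 1 or more therapeutic corneal transplants".

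**The concern.** A therapeutic graft or keratectomy removes diseased cornea. If the eye is quiet afterwards, the slit-lamp findings reflect the operation at least as much as the drops. A rule that reads only the findings and the relapse answer cannot tell the two apart, and the plan gives no other instruction.

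Two things are at stake. First, drug failure rescued by surgery could enter the primary comparison as success, and in a trial of this size a few eyes matter. Second, the margin rests on a historical rate in which transplanted patients were not counted as cured. If grafted eyes can count in CRR_12, the trial endpoint and the rate behind the margin do not measure the same thing.

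**Working it through.** **1. Can an operated eye pass every written condition?** Take a subject with therapeutic keratoplasty or keratectomy on study.

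- *Does surgery force exit?* No. It is not a failure box, a 5.3.4 item or a 4.4 reason. Protocol 8.1.4 says procedures are not themselves adverse events, so surgery does not by itself trigger the adverse-event route.
- *Is there a written path that keeps such a subject in?* Yes. Box II counts melting and ulceration among the signs of relapse, and a culture-negative relapse within 11 months restarts treatment in the trial (Boxes XI and XIII).
- *Does the scoring rule stop it later?* No. CRYN = Yes by day 365, no later relapse and no discontinuation are sufficient.
- *Does the per-protocol set stop it?* Not by rule. SAP 7.4 lists non-compliance with treatment and missed follow-up visits. Anything further is left to the clean file meeting.

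So the classification is possible as written.

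**2. The plan's own figures.** Inputs: 63% v 83%, two-sided alpha 0.10, power 80%, 10% loss (Protocol 7.6, SAP 5.1).

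- n per arm = [0.63×0.37 + 0.83×0.17] × (1.645 + 0.842)² / 0.20² = 57.8, so 58 per arm and 116 evaluable. 116/0.9 = 128.9, stated as 130. This reproduces.
- Table 1: the exact lower bound for 63/100 is 0.528, rounded to 0.53. M1 = 0.53 − 0.05 = 0.48, and (0.48 − 0.20)/0.48 = 58%. This reproduces.

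**3. Weight of one eye.** 1/65 = 1.5 points on randomised numbers; 1/58 = 1.7 points on evaluable numbers. For an assumed excess of 1 to 5 eyes in one arm, the difference shifts by 1.5 to 7.7 points (n = 65) or 1.7 to 8.6 points (n = 58).

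**4. Effect at the decision boundary.** Assume 37/58 control cures (0.638) and use the 90% Wald interval.

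- 35/58 test: difference −0.034, SE = √[(0.603×0.397 + 0.638×0.362)/58] = 0.0900. Lower limit −0.034 − 1.645×0.0900 = −0.183. Non-inferiority is met.
- 34/58 test: difference −0.0517, SE = √[(0.586×0.414 + 0.638×0.362)/58] = 0.0904. Lower limit −0.0517 − 0.1486 = −0.2003. Non-inferiority is lost.

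In this example, rescoring one test-arm eye changes the conclusion.

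**5. Assumed excess of surgical cures** (58 per arm; 5 points is 2.9 eyes, 10 points is 5.8 eyes).

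| Excess in | Quantity | 0 points | 5 points | 10 points |
|---|---|---|---|---|
| Test arm | One-sided non-inferiority error, true medical cure 63% v 43% | 5.0% | 13.6% | 29.2% |
| Control arm | Superiority power, 63% v 83% | 78.9% | 59.4% | 36.4% |

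The error is Φ[(d + 0.20)/SE − 1.645], where d is the apparent difference. Power uses the pooled-variance test. If both arms gain 5 points (68% v 88%), power is 83.8%, so an equal gain in both arms does not cost power here.

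**6. Match with the margin.** The value 1/20 cannot include the 14 transplanted patients. If every grafted patient were counted as cured, the upper bound would be (3 + 14)/20 = 0.85 and M1 = 0.53 − 0.85, which is negative. This is a bound and not an estimate. It shows that the margin presupposes grafts are not cures.

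**The case against.** **Most such eyes may already fail or exit.** Box VIII covers enlarging ulcer, stromal thinning and ring abscess, and continued deterioration after that is failure. Culture-positive relapse is failure. An investigator may withdraw a subject, and withdrawn subjects count as not cured. This stands as a limit on how often the gap is used. It does not close the gap, because each step rests on judgement and surgery triggers none of them.

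**An operated eye may not meet the criteria.** The epithelium must be healed, with no corneal inflammation needing treatment and a quiet anterior chamber. No document says grafted eyes reach this state, and none says they cannot. For eviscerated or enucleated eyes the objection is decisive: they cannot meet slit-lamp criteria, so the point is confined to keratoplasty and keratectomy, with amniotic membrane and glue less clear.

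**The historical series is mixed.** One of its three medical cures was grafted, so it does not treat every transplant as a bad outcome. That is fair, but the 14 are still outside the 1/20.

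**Bias towards non-inferiority.** A reader might infer that the gap pulls the arms together and favours non-inferiority. The documents do not support that. It favours non-inferiority only if the test arm has more surgery; if the control arm has more, it works against the test drug. Nor do the documents say that CRR_12 measures cure by drops alone. Scoring surgery as non-response is a choice, though it is the one that matches the margin.

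**Unseen sources.** Figure 2 is not visible in the text reviewed, and the Study Operations Manual and Data Display Plan were not available. The written legend to Figure 2 contains no surgical rule.

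**Conclusion.** The gap is real. Under SAP 7.9.1 as written, a study eye that had therapeutic penetrating or lamellar keratoplasty, or therapeutic keratectomy, is a CRR_12 success if the subject remains in the study with CRYN = Yes by day 365 and no later relapse. This also conflicts with the historical rate that supports the 0.20 margin.

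Its size is 1.5 to 1.7 points per eye. How many eyes are involved, and in which arm, cannot be learned from the documents, and the ranges above are assumptions. A reader might conclude that surgical rescue will commonly be scored as cure, or that the margin or the sample size is wrong. Neither follows: many operated eyes would probably exit first, and the plan's sample size and Table 1 reproduce. The conclusion is narrower. The primary endpoint has an unscored intercurrent event, and one eye can matter near the boundary.

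**What to change.** Before unmasking:

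1. **State the scoring rule in SAP 7.9.1.** For example: *For scoring only, a subject who has therapeutic penetrating or lamellar keratoplasty, or therapeutic keratectomy, of the study eye before the 30-day off-therapy assessment is not cured for CRR_12, whatever CRYN records.*
2. **State the time-to-cure rule.** Such a subject has no event, stays in the risk set to day 365 and is not censored at surgery. Censoring at surgery would be informative. SAP 7.9.3 and 8.3 need a matching sentence.
3. **Issue a matching protocol amendment.** SAP section 2 requires one when a principal feature changes, and the cure definition is such a feature.
4. **Identify procedures by masked review** of CMTRT at the clean file meeting, recording the eye, date and purpose. CMTRT holds names of any drug or therapy, so a simple data pull may not separate therapeutic from other procedures.
5. **Add one sensitivity analysis** that also counts amniotic membrane, glue, and surgery between the 30- and 90-day visits as not cured.

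The cost is a short amendment, one masked listing review and one extra analysis. CRR_12 may be slightly lower in both arms. Sample size is unchanged, and no change to clinical management is proposed.
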